2 DEFINITION OF ANALYSIS SETS

2.1 Study Design and Number of Patients

The study has a total of 4 dosing combinations:

- Osimertinib (80 mg od + savolitinib (300 mg od) (explored under Clinical Study Protocol [CSP] versions 1.0 to 4.0)
- Osimertinib (80 mg od) + savolitinib (300 mg bid) (explored under CSP versions 5.0 to 7.0)
- Osimertinib (80 mg od) + savolitinib (600 mg od) (explored under CSP versions 1.0 to 2.0 and reintroduced under CSP versions 5.0 to 6.0)
- Placebo to osimertinib + savolitinib (300 mg bid) (explored under CSP version 7.0)

The savolitinib 300 mg od [Once daily] regimen was originally sized to ensure there were sufficient patients in each of the diagnostic populations. Approximately **[CC1]** centrally confirmed Hepatocyte growth factor receptor [MET] Fluorescence in situ hybridisation+ [FISH+] patients were planned to be treated with osimertinib 80 mg od plus savolitinib 300 mg od. To achieve **[CC1]** centrally confirmed MET FISH+ patients at this dose, it was anticipated that **[CC1]** patients at this dose would be treated in this study, assuming **[CC1]** of these would be centrally confirmed FISH+ patients and **[CC1]** (**[CC1]** patients) would be centrally confirmed MET Immunohistochemistry+ [IHC+] patients. As the overall prevalence rates and the level of concordance between FISH and IHC methods may vary and a small number of patients recruited by pre-existing Next generation sequencing [NGS] may not have a central confirmation, it was anticipated that greater or less than **[CC1]** patients would be required to achieve **[CC1]** centrally confirmed MET FISH+ patients, however this was not expected to exceed **[CC1]** treated patients at this dose. If the proportion of patients who had central confirmation by IHC was lower than expected, additional patients were to be recruited to ensure there were at least **[CC1]** centrally confirmed MET IHC+ patients.

Under CSP version 5.0, approximately **[CC1]** patients (post First-line [1L] or Second-line [2L] osimertinib) were planned to be randomised in a 2:1 ratio to receive osimertinib 80 mg od in combination with either savolitinib 300 mg bid (approximately **[CC1]** patients) or savolitinib 600 mg od (approximately **[CC1]** patients). Since **[CC1]** patients had already received the 600 mg od dose (enrolled prior to CSP version 5.0,

under the previous weight- based dosing schedule), approximately **[CC1]** patients in total were planned to receive osimertinib in combination with savolitinib 600 mg od.

Under CSP version 6.0, the enrolment was further restricted to post 1L osimertinib and central MET FISH+ only, therefore approximately **[CC1]** patients that were planned to be randomised in a 2:1 ratio to osimertinib 80mg od in combination with either savolitinib 300 mg bid or savolitinib 600 mg od applied to the new population (ie, post 1L osimertinib and central MET FISH+).

Under CSP version 7.0, approximately **[CC1]** patients (post 1L osimertinib with MET amplification/overexpression [FISH10+ and/or IHC90+] will be randomised in a 2:1 ratio to receive savolitinib 300 mg bid + osimertinib 80 mg (approximately **[CC1]** patients) or savolitinib 300 mg bid + placebo to osimertinib (approximately **[CC1]** patients). With assumed objective response rates [ORRs] of

CCI and CCI, for the savolitinib 300 mg bid + osimertinib 80 mg and the savolitinib 300 mg bid + placebo arms respectively, there will be at least CCI power at a 2-sided 0.05 significance level to detect a difference in ORRs of the 2 arms.

Overall, approximately CCI to CCI patients are anticipated to be pre-screened for MET-amplified/overexpressed status in this study.

All patients confirmed as eligible will begin treatment on Day 1 with osimertinib + savolitinib combination therapy or placebo to osimertinib + savolitinib. Treatment will continue in 28-day cycles until objective disease progression by investigator per Response Evaluation Criteria in Solid Tumours [RECIST] 1.1 is assessed, unacceptable toxicity, withdrawal of consent or another discontinuation criterion is met.

Under CSP version 7.0 only, at investigator-assessed progressive disease [PD] per RECIST 1.1, treatment allocation will be unblinded and those patients randomised to the savolitinib plus placebo arm will have the opportunity to cross over to the savolitinib plus osimertinib regimen.

To be noted, all patients treated with savolitinib 300 mg od or 600 mg od indiscriminately of CSP versions will be analysed all together (e.g. all 300 mg od or all 600 mg od, respectively).

Primary and final analyses:

For the savolitinib 300 mg bid dosing regimen, with approximately CCI patients (approximately CCI patients under CSP version 7.0 and approximately CCI patients under CSP version 5.0 and version 6.0) with FISH10+ and/or IHC90+ status who have progressed following 1L osimertinib treatment, Confidence intervals [CIs] will be provided and be compared with the historical reference platinum-pemetrexed chemotherapy ORR of approximately CCI.

For the savolitinib 300 mg od dosing regimen, with approximately CCI patients with FISH5+ and/or IHC50+ status who have progressed following osimertinib treatment, there will be at least CCI power for an exact binomial test with a two-sided significance level of 0.05 to detect a difference between the null hypothesis proportion of CCI and the alternative hypothesis proportion of CCI.

For the centrally confirmed IHC+ and all patient populations at the savolitinib 300 mg od dosing regimen, with CCI and CCI patients there would be CCI and CCI power, respectively, to detect a difference.

For interim analyses:

Please refer to Section 5.

2.2 Analysis Sets

The analysis sets are presented in [Table 2](#).

Patients will be assigned to each of the populations in Table 2 and to the diagnostic populations (centrally confirmed by FISH [FISH5+, FISH10+] and centrally confirmed by IHC [IHC50+, IHC90+]), prior to any analyses being performed. Additional details on diagnostic populations can be found in section [4.1](#).

Table 2 Analysis Sets

Analysis Set	Definition
Target Population Analysis Set (TPAS)	All patients assigned to savolitinib 300 mg bid + osimertinib who have FISH10+ and/or IHC90+ status, have progressed following 1L osimertinib, and have taken ≥ 1 dose of either study drug.
Contribution of Components Analysis Set (CAS)	All patients randomised under CSP version 7.0 with treatment groups assigned in accordance with the randomisation, regardless of the treatment actually received.
Safety Analysis Set (SAF)	All enrolled patients who take ≥ 1 dose of either study drug.
PK Analysis Set	All patients who receive at least 1 dose of savolitinib or osimertinib as per the protocol for whom any post-dose PK data are available and do not violate or deviate from the protocol in ways that would significantly affect the PK analyses will be included in the PK analysis set.
Evaluable for Response	Dosed patients who have measurable disease at baseline. This population will only be used for interim analyses.
Evaluable for Response 2	Dosed patients with measurable disease at baseline who have had the opportunity for 2 on-treatment RECIST scans. This population will only be used for interim analyses.
Safety Analysis Set 2 (SAF2)	All enrolled patients who take ≥ 1 dose of either study drug who have had the opportunity to be treated for 6 weeks. This population will only be used for interim analyses.

CSP Clinical study protocol; FISH Fluorescence in situ hybridisation; IHC immunohistochemistry; PK Pharmacokinetic(s); RECIST Response Evaluation Criteria in Solid Tumor.

If during the study a patient stops one of the two study treatments and continues on monotherapy or a patient crossover to the combo treatment, the data for the patient will continue to be treated as per the initial treatment allocation.

For the Pharmacokinetic [PK] analysis set, where a protocol deviation impacts only part of a patient's data, the affected portion of the patient's PK data will be excluded from PK analysis and summary statistics, and the remaining valid data will be utilised.

The Target Population Analysis Set (TPAS) will be used as the population for reporting efficacy and to summarise baseline characteristics for patients dosed with savolitinib 300 mg bid + osimertinib who are FISH10+ and/or IHC90+ and have progressed following treatment with 1L osimertinib (primary endpoint population).

The Contribution of Components Analysis Set (CAS) will be used as the population for reporting efficacy and to summarise baseline characteristics for patients randomised under CSP version 7.0.

The Safety Analysis Set (SAF) will be used for reporting efficacy of savolitinib 300 mg od + osimertinib in FISH5+ and/or IHC50+ patients (primary endpoint population). The SAF will also be used as the population for reporting efficacy and to summarise baseline characteristics for patients dosed under all CSP versions. The SAF will be used as the population for reporting safety for patients dosed under all CSP versions.

The PK analysis set will be used for reporting PK for patients dosed under all CSP versions. For the PK analysis set, where a protocol deviation impacts only part of a patient's data, the affected portion of the patient's PK data will be excluded from PK analysis and summary statistics, and the remaining valid data will be utilised.

Table 3 Summary of outcome variables, analysis sets and MET Status.

Outcome Variable	Analysis set and Doses	MET status
Demography and baseline characteristics	TPAS Savolitinib 300 mg bid + osimertinib SAF Savolitinib (300 mg od, 300 mg bid, 600 mg od) + osimertinib Savolitinib (300 mg od, 300 mg bid, 600 mg od) + osimertinib Savolitinib 300 mg bid + placebo CAS Savolitinib 300 mg bid + osimertinib Savolitinib 300 mg bid + placebo	FISH10+ and/or IHC90+ FISH5+ and/or IHC50+ FISH10+ and/or IHC90+ FISH10+ and/or IHC90+
Exposure	TPAS Savolitinib 300 mg bid + osimertinib SAF Savolitinib (300 mg od, 300 mg bid, 600 mg od) + osimertinib Savolitinib (300 mg od, 300 mg bid, 600 mg od) + osimertinib Savolitinib 300 mg bid + placebo	FISH10+ and/or IHC90+ FISH5+ and/or IHC50+ FISH10+ and/or IHC90+

Primary Objective	Endpoint	Analysis set and Doses	MET status
Primary endpoint			
Efficacy Data			
To determine the efficacy of savolitinib (300 mg bid) in combination with osimertinib in patients with EGFRm+ and MET amplified/overexpressed (FISH10+ and/or IHC90+) ^a , locally advanced or metastatic NSCLC who have progressed following treatment with 1L osimertinib	ORR by investigator assessment in accordance with RECIST 1.1.	TPAS Savolitinib 300 mg bid + osimertinib	FISH10+ and/or IHC90+
To determine the efficacy of savolitinib (300 mg od) in combination with osimertinib in patients with EGFRm+, MET amplified/overexpressed (FISH5+ and/or IHC50+) ^b , locally advanced or metastatic NSCLC who have progressed following osimertinib.	ORR by investigator assessment in accordance with RECIST 1.1.	SAF Savolitinib 300 mg od + osimertinib	FISH5+ and/or IHC50+
Secondary Objective	Endpoint	Analysis set and Doses	MET status
Secondary endpoints			
Efficacy Data			
To determine the efficacy of savolitinib (300 mg bid) in combination with osimertinib in patients with EGFRm+ and MET amplified/overexpressed (FISH10+ and/or IHC90+) ^a , locally advanced or metastatic NSCLC who have progressed following treatment with 1L osimertinib.	DoR and PFS by investigator assessment in accordance with RECIST 1.1 OS	TPAS Savolitinib 300 mg bid + osimertinib	FISH10+ and/or IHC90+

To describe the difference in the efficacy of savolitinib (300 mg bid) in combination with osimertinib and savolitinib (300 mg bid) in combination with placebo in patients with EGFRm+, MET amplified/overexpressed (FISH10+ and/or IHC90+)^a, locally advanced or metastatic NSCLC who have progressed following treatment with 1L osimertinib therapy under CSP version 7.0.
	
ORR by investigator assessment in accordance with RECIST 1.1
	
CAS Savolitinib 300 mg bid + osimertinib Savolitinib 300 mg bid + placebo
	
FISH10+ and/or IHC90+

To determine the efficacy of savolitinib (300 mg od and 600 mg od, respectively) in combination with osimertinib in patients with EGFRm+, MET- amplified/overexpressed (FISH10+ and/or IHC90+)^a, locally advanced or metastatic NSCLC who have progressed following treatment with 1L osimertinib.
	
ORR, DoR, and PFS, by investigator assessment in accordance with RECIST 1.1. OS
	
SAF Savolitinib (300 mg od, 600 mg od) + osimertinib
	
FISH10+ and/or IHC90+

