9.4 Statistical analyses

9.4.1 General considerations

Analyses will be performed by AstraZeneca or its representatives. A comprehensive SAP will be developed and will describe the patient populations to be included in the analyses and procedures for accounting for missing, unused and spurious data. This section is a summary of the planned statistical analyses of the primary and secondary endpoints. Any deviations from this plan will be reported in the clinical study report.

Descriptive statistics will be used for all variables. Continuous variables will be summarised by the number of observations, mean, standard deviation, median, minimum and maximum. Categorical variables will be summarised by frequency counts and percentages for each category. Unless otherwise stated, percentages will be calculated out of the population total.

Analyses will be presented by the assigned starting dose (300 mg od savolitinib, 300 mg bid savolitinib and 600 mg od savolitinib in combination with osimertinib, or 300 mg bid savolitinib as monotherapy [savolitinib + placebo]).

Additional subgroup analyses of efficacy and safety may be performed and will be specified in the SAP.

Depending on the extent of any impact, summaries of data relating to patients diagnosed with COVID-19, and impact of COVID-19 on study conduct (in particular missed visits, delayed or discontinued study intervention, and other protocol deviations) may be generated. More detail will be provided in the SAP.

Baseline for patients allocated/ randomised to treatment will be the last assessment of the variable under consideration prior to the intake of the first dose, except for efficacy variables. For efficacy variables, baseline is defined as the last visit prior to randomisation (patients enrolled under CSP version 7.0) or last visit prior to first dose (patients enrolled prior to CSP version 7.0). For patients who cross over from savolitinib plus placebo to savolitinib plus osimertinib, their data will be cut off for the purposes of any savolitinib plus placebo assessment at the last assessment of the variable under consideration prior to the intake of the first dose of the combination therapy.

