3 DESCRIPTION OF VARIABLES

3.1 General principles

3.1.1 Baseline measurements and change from baseline variables

Baseline for patients allocated/randomised to treatment will be the last assessment of the variable under consideration prior to the intake of the first dose, except for efficacy variables. For efficacy variables, baseline is defined as the last non-missing assessment prior to randomisation (patients enrolled under CSP version 7.0) or last non-missing assessment prior to first dose (patients enrolled prior to CSP version 7.0). For patients who cross over from savolitinib plus placebo to savolitinib plus osimertinib, their data will be cut off for the purposes of any savolitinib plus placebo assessment at the last assessment of the variable under consideration prior to the intake of the first dose of the combination therapy.

If two assessments are equally eligible to assess patient status at baseline (e.g. on the same date prior to first dose with no time recorded to distinguish the assessments), the average should be taken as the baseline value. For non-numeric laboratory tests (i.e. some of the urinalysis parameters) where taking an average is not possible then the best value would be taken as baseline as this is the most conservative. In the scenario where there are two assessments on Day 1, one with time recorded and the other without time recorded, the one with time recorded would be selected as baseline, assuming it could be determined that it occurred prior to first dose. Where safety data are summarised over time, study day will be calculated in relation to date of first treatment. If no value exists before the first dose/administration, then the baseline value will be treated as missing.

Regarding electronic Patient reported outcome [ePRO] questionnaires, the baseline is defined as the non-missing assessment collected at Day 1, as it is assumed it is taken prior to start of the study treatment. If an assessment is missing at Day 1, the prior non-missing assessment will be used as baseline.

In all summaries change from baseline variables will be calculated as the post treatment value minus the

value at baseline. For % change from baseline, calculate:

$$\% \text{ change from baseline} = \frac{(\text{Post baseline value} - \text{Baseline Value})}{\text{Baseline value}} \times 100$$

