On treatment period includes a safety follow-up period following discontinuation of both study treatments of 28+7 days. Therefore, discontinuation visit and follow up [FUP] visit will be slotted into the appropriate analysis visit using the time windowing described in Table 5. Assessments performed after 28+7 days from final dose (i.e., outside the on-treatment period) will be labelled as 'Post follow-up' and they will be only listed.

Unscheduled visit data will be considered when assigning assessments to the analysis visit. If more than one assessment of the variable (scheduled or unscheduled) falls in the same time window but on different days, the closest to the scheduled visit day will be taken, or the earlier, in the event the values are equidistant from the nominal visit date. If several measurements are collected during the selected day, the average (for numeric values)/worst (for categorical values) of the measurements will be taken.

In summaries of extreme values as opposed to visit-based summaries, all post baseline values collected are used including those collected at unscheduled visits regardless of the value being closest to the scheduled visit date or not. For summaries at a patient level, all values should be included, regardless of whether they appear in a corresponding visit-based summary, when deriving a patient level statistic such as a maximum.

Listings will display all values contributing to a time point for a patient.

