3.2.2.3 Adverse Events

An AE is defined as the development of any untoward medical occurrence in a patient or clinical study patient administered a medicinal product, and which does not necessarily have a causal relationship with this treatment. The term AE is used to include both serious and non-serious AEs and can include a deterioration of a pre-existing medical occurrence.

AEs and Serious adverse events [SAEs] will be collected from the time of signing of the main study Informed consent form [ICF] throughout the treatment period and including the follow-up period. The follow-up period is defined as 28+7 days after study treatment is discontinued.

AEs will be defined as treatment emergent adverse events [TEAEs] if they have an onset or worsen (by investigator report of a change in severity) during the study treatment period (defined from date of first dose of any study treatment to date of last dose of any study treatment) or safety follow-up period (28 days [+7 days] after last dose of study treatment). Any events in this period that occur after a patient has received further therapy for cancer (following discontinuation of study treatments) will be flagged in the data listings. AEs with a missing start time which occur on the same day as first IP administration will be reported as on-treatment.

The Medical Dictionary for Regulatory Activities [MedDRA] (version 21.0 or later) will be used to code the AEs. AEs will be graded according to the National Cancer Institute Common Terminology Criteria for AEs [CTCAE Version 5 or later].

Other significant adverse events [OAE]

During the evaluation of the AE data, an AstraZeneca medically qualified expert will review the list of AEs that were not reported as SAEs and AEs leading to discontinuation. Based on the expert's judgement, significant AEs of particular clinical importance may, after consultation with the Global Patient Safety Physician, be considered other significant adverse events and reported as such in the clinical study report. A similar review of laboratory/vital signs/ Electrocardiogram [ECG] data and other safety assessments will be performed for identification of other significant adverse events. This review will take place at least prior to primary and final analyses and prior to database lock, and any AEs identified will be fully documented in meeting minutes.

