- TEAEs leading to discontinuation of each study treatment (overall and within the first 6 weeks)
- TEAEs leading to discontinuation of each study treatment - key patient information
- Other significant TEAEs
- Other significant TEAEs leading to discontinuation of each study treatment (overall and within the first 6 weeks)
- TEAEs of special interest
- TEAEs of special interest by CTCAE grade
- TEAEs of special interest leading to discontinuation of each study treatment (overall and within the first 6 weeks)
- Hypersensitivity/anaphylaxis and hepatotoxicity TEAEs of special interest leading to discontinuation of savolitinib (overall and within the first 6, 12 and 24 weeks)

An overall summary table of the number of patients experiencing at least one adverse event will be produced. An overall summary table of the number of AEs will also be provided.

TEAEs in any category, including AESI, TEAEs of CTCAE grade ≥ 3 , deaths, SAEs, TEAEs leading to discontinuation, and other significant TEAEs will be summarised.

AEs occurring prior to first dose of study treatments (i.e., before study Day 1) which subsequently worsen in severity following dosing will be presented in the summary tables. All other AEs occurring prior to first dose of study treatments (i.e., before study Day 1), or after the 35-day follow-up period (28 days allowing for the ± 7 -day window) after discontinuation of study treatments will be listed, but not included in the summaries.

Details of any deaths will be listed for all patients.

All AEs will be listed, and any AEs started on or after a patient took osimertinib after crossing over from 300 mg bid + placebo to 300 mg bid + osimertinib will be flagged.

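### SAP 2.2 keeps crossover patients' data under their initial arm while SAP 3.1.1 and Protocol 9.4.1 cut them off, so combination-period safety data can be reported as savolitinib monotherapy

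*SAP*

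**What the plan says.** Two rules govern patients randomised to savolitinib + placebo who later receive osimertinib.

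- **SAP 2.2 (Analysis Sets):** if "a patient crossover to the combo treatment, the data for the patient will continue to be treated as per the initial treatment allocation". The sentence is not confined to one analysis set or to efficacy.
- **SAP 3.1.1:** for the same patients, "their data will be cut off for the purposes of any savolitinib plus placebo assessment at the last assessment of the variable under consideration" before the first combination dose. **Protocol 9.4.1** has the same rule: "their data will be cut off for the purposes of any savolitinib plus placebo assessment".

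The safety sections then set their own windows.

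- **SAP 3.1.3:** "On treatment period includes a safety follow-up period following discontinuation of both study treatments of 28+7 days". For extremes: "In summaries of extreme values as opposed to visit-based summaries, all post baseline values collected are used".
- **SAP 3.2.2.3:** the treatment period for treatment-emergent events is "defined from date of first dose of any study treatment to date of last dose of any study treatment", plus follow-up.
- **SAP 4.2.3.2:** events before first dose (unless they worsen after dosing), or after the 35-day period "after discontinuation of study treatments will be listed, but not included in the summaries". The listing rule flags "any AEs started on or after a patient took osimertinib after crossing over".
- **SAP 3.2.2.1:** total treatment duration runs to the last non-zero dose in the log, death or data cut-off, whichever is earliest.

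SAP 4.2.3 reports the savolitinib + placebo arm as the monotherapy safety group. Protocol 4.1.2 requires savolitinib to continue without a break through crossover.

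**The concern.** The savolitinib + placebo column is the only monotherapy safety column in the SAP. The two crossover rules give different adverse event incidences, extreme values and exposure times from the same data, and the SAP does not say which prevails.

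QTcF shows the problem. Protocol Appendix I 3.5 recognises QT prolongation as a toxicity of both drugs. SAP 4.2.3.4 counts QTcF above its thresholds at any time during treatment, so a value recorded after osimertinib is added could be reported as a monotherapy value.

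There is a narrower efficacy consequence. Under SAP section 5, futility means that no responses were seen among the first savolitinib + placebo patients. Patients who then cross over without progression keep having scheduled scans. Under SAP 2.2, a response on the combination could enter the ORR of the arm that was just declared futile.

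**Working it through.** The plan gives no figure to reproduce. The number of crossovers is not stated and the arm sizes are redacted. The check is a trace of the rules, followed by ranges under stated assumptions.

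**Safety**

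1. *Adverse events.* The treatment-emergent window closes after the last dose of any study treatment. Savolitinib continues through crossover, so the window stays open. SAP 4.2.3.2 names the events that are listed but not summarised, and post-crossover events are not among them. They are only flagged in a listing.
2. *ECG, laboratory, vital signs.* The on-treatment period ends 28+7 days after both drugs stop, and extreme-value summaries use all post-baseline values. This reaches QTcF categories, maximum laboratory grade (SAP 4.2.3.6) and minimum/maximum vital signs (SAP 4.2.3.5). ECG and laboratory listings carry a crossover flag; none is stated for vital signs.
3. *Exposure.* Duration runs through crossover. The added time is true savolitinib exposure but not monotherapy exposure.

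**Efficacy**

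4. *Investigator ORR in the Contribution of Components Analysis Set (CAS).* ORR data stop at progression (SAP 3.2.1.1.2), so crossover at investigator-assessed progression has no effect. Crossover without progression after futility does. The stop at subsequent therapy misses it, because SAP 3.2.2.4 defines such therapy as starting after the last dose of study treatment.
5. *Central review (BICR) and CNS endpoints.* The central reviewers receive all scans, so ORR and DoR by BICR and the CNS endpoints need the same cut-off.
6. *PFS and DoR.* The PFS definition (Protocol 9.4.3.2, SAP 3.2.1.1.5) follows patients regardless of other anti-cancer therapy. Protocol 9.4.1 cuts them off at crossover. The two are not reconciled.
7. *Not affected.* Both primary ORRs, the patient-reported outcomes and the tumour-size summaries contain no savolitinib + placebo column.

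**Illustrative size**

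*Adverse event incidence.* Excess points = 100 × c × (1 − p_mono) × p_post. Here c is the fraction crossing over (assumed 0.25 to 0.75), p_mono is the incidence on monotherapy, and p_post is the fraction of those still event-free with a first event after crossover (assumed 0.05 to 0.20).

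| p_mono | Low: c 0.25, p_post 0.05 | High: c 0.75, p_post 0.20 |
|---|---|---|
| 0.10 | 100 × 0.25 × 0.90 × 0.05 = 1.1 | 100 × 0.75 × 0.90 × 0.20 = 13.5 |
| 0.50 | 100 × 0.25 × 0.50 × 0.05 = 0.6 | 100 × 0.75 × 0.50 × 0.20 = 7.5 |
| 0.90 | 100 × 0.25 × 0.10 × 0.05 = 0.1 | 100 × 0.75 × 0.10 × 0.20 = 1.5 |

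*Arm-mean savolitinib duration.* Ratio = 1 + c × post/pre, with the same time before crossover or stopping for every patient (assumed).

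- 12 weeks before, 24 after: 1 + 0.25 × 2 = 1.5; 1 + 0.50 × 2 = 2.0; 1 + 0.75 × 2 = 2.5.
- 24 before, 6 after, c = 0.25: 1 + 0.25 × 0.25 = 1.06.
- 6 before, 36 after, c = 0.75: 1 + 0.75 × 6 = 5.5.

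*Investigator ORR in the CAS.* Excess points = 100 × s × r, where s is the fraction of the arm crossing over without progression and r is their response rate.

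- No futility declaration: s = 0, excess 0.
- s = 0.05, r = 0.20: 1.0 point.
- s = 0.20, r = 0.55: 11.0 points. The 55% is the combination ORR assumed in Protocol 9.2; s and the lower r are assumptions.

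**The case against.** The strongest reply is that the rules are compatible. The full sentence in SAP 2.2 also covers patients who stop one drug and continue on the other, and it sits under Analysis Sets. It can be read as fixing the arm label, with SAP 3.1.1, a general principle, deciding how much of the data counts. ECG, laboratory, vital-sign and tumour results are naturally assessments of a variable, so 3.1.1 may already trim them. SAP section 6 lists no departure from Protocol 9.4.1, which fits that reading. Crossover also has its own schedule (Protocol Table 2), and SAP 4.2.3 allows a dedicated version 7.0 safety analysis.

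Part of this stands. The label-only reading is possible, and for ECG, laboratory and vital signs a careful programmer could reach the right result. But 2.2 speaks of the data, not the label, and the all-values rule in 3.1.3 points the other way. For adverse events and exposure the reading gives no rescue: they fit poorly under an assessment rule in a section on baseline, and their own sections have no crossover stop. If 3.1.1 does not reach them, 2.2 and the open window are all that remains in the SAP. The flags affect listings only, and the dedicated analysis is optional.

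Three further points are fair. The ORR effect depends on a futility declaration that nothing in the documents reports, and that comparison is secondary and descriptive. The ranges rest on assumptions, and the 55% was assumed for patients randomised to the combination, not for those crossing over. Following survival under the randomised arm is a legitimate use of 2.2 and should be preserved.

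**Conclusion.** The concern holds and should be fixed. SAP 2.2 conflicts with SAP 3.1.1 and Protocol 9.4.1. As the safety sections stand, adverse events and exposure on the combination enter the monotherapy column. For ECG, laboratory and vital-sign extremes the SAP points both ways.

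The conflict itself rests on the text alone. Its size does not: crossover numbers, time on the combination and arm sizes are unavailable, so the calculated ranges only illustrate what is possible. Across the assumptions used, incidence rises by 0.1 to 13.5 points and mean savolitinib duration by 1.06- to 5.5-fold. More post-crossover data can accrue by the final analysis, at 15 months after the last randomisation, than by the primary analysis at 6 months. Investigator ORR in the CAS is unchanged without a futility declaration, and both primary ORRs are unchanged in any case.

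**What to change.** Amend SAP 2.2 to keep the allocated arm label and to apply the cut-off of SAP 3.1.1 and Protocol 9.4.1 explicitly:

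- **Safety and exposure.** End savolitinib + placebo summaries of treatment-emergent events, exposure, laboratory, ECG and vital signs before the first crossover osimertinib dose. Tabulate later data separately and add a listing flag for vital signs.
- **Response.** In the savolitinib + placebo arm of the CAS, count only assessments before that dose for ORR and best response by investigator, BICR and CNS review. Require both the initial and the confirmatory scan before it, as SAP 3.2.1.1.2 already does for subsequent therapy.
- **PFS and DoR.** For crossover without progression, the sponsor should reconcile the cut-off with the PFS definition and state the choice. If either endpoint continues past crossover, list that in SAP section 6 as a departure from Protocol 9.4.1.
- **Survival.** State that survival follow-up stays with the randomised arm.

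The cost is SAP wording, one extra safety column and possibly a section 6 entry. The first-osimertinib date is already needed for the listing flags. There are three downsides: monotherapy exposure time is shorter, late monotherapy events that start after crossover move to the post-crossover column, and a response unconfirmed at crossover no longer counts.
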